METC	Medical research ethics committee (MREC); in Dutch: medisch ethische toetsing commissie (METC)
(S)AE	(Serious) Adverse Event
SPC	Summary of Product Characteristics (in Dutch: officiële productinformatie IB1-tekst)
Sponsor	The sponsor is the party that commissions the organisation or performance of the research, for example a pharmaceutical company, academic hospital, scientific organisation or investigator. A party that provides funding for a study but does not commission it is not regarded as the sponsor, but referred to as a subsidising party.
SUSAR	Suspected Unexpected Serious Adverse Reaction
Wbp	Personal Data Protection Act (in Dutch: Wet Bescherming Persoonsgegevens)
WMO	Medical Research Involving Human Subjects Act (in Dutch: Wet Medisch-wetenschappelijk Onderzoek met Mensen)

SUMMARY

Rationale: In gastrointestinal cancer patients, overall almost 30% of patients experience severe fatigue while in HPB cancer the vast majority suffers from fatigue. Generally, even after successful cancer treatment, 19 to 38% of disease-free cancer survivors remain fatigued, which underlines its persistent character. The cancer itself, as well as the sequelae after surgical interventions or chemotherapy may lead to physical and psychosocial impairment in cancer patients. As patients experience increased fear and a lower exercise tolerance due to persistent fatigue they are at great risk of spiralling down a vicious circle which progressively enhances these symptoms and further impairs their quality of life and self-management capacity. In patients who have been treated for cancer, psychotherapy and physical exercise are shown to reduce fatigue complaints.

Objective: Since multiple dimensions (physical, emotional and cognitive) seem to be involved in the pathophysiology of fatigue, multidimensional approach to alleviate will probably have a synergistic effect. Previous studies supporting this assumption included general cancer populations or breast and colon cancer patients, who are known for their relatively good prognosis and post-treatment functional outcome.

The purpose of our study is to investigate whether a postoperative rehabilitation program (solution focused psycho- and physical exercise therapy) improves fatigue (primary outcome) and quality of life, muscle mass, and physical fitness (secondary outcomes) in cancer patients operated for HPB malignancies, known to have a more dismal prognosis.

Study design: In this multicentre randomized controlled trial, patients will randomly be assigned to the treatment (rehabilitation program) or control (usual care) group in the four participating centres. After hospital discharge, the treatment group will undergo a supervised, tailored exercise program aimed at both cardiorespiratory fitness (aerobic training) and muscle strength (resistance training) twice a week during twelve weeks. Furthermore, one hour solution focused therapy is offered every other week. The primary outcome will be MFI-General Fatigue, at 12 months after surgery. Secondary outcomes are quality of life, cardiopulmonary fitness, skeletal muscle mass and strength, distribution and intensity of physical activity, MFI-Physical Fatigue, MFI-Mental Fatigue, MFI-reduced activity and motivation, frailty, anxiety, depression, and body weight, and risk of malnutrition assessed preoperatively, at the start and end of the rehabilitation program and six and twelve months after surgery. Validated tests are used to assess these parameters. Furthermore, an effect of the intervention on overall survival will be investigated.

Study population: Adult HPB cancer patients undergoing surgical cancer resection in Erasmus MC (Rotterdam), AMC (Amsterdam), LUMC (Leiden), and UMCG (Groningen) will be included in this study.

Intervention (if applicable): rehabilitation program consisting of physical exercise therapy, psychotherapy and dietary consultation.

Main study parameters/endpoints: General fatigue, assessed with the Multidimensional Fatigue Inventory (MFI).

Nature and extent of the burden and risks associated with participation, benefit and group relatedness: None.

INTRODUCTION AND RATIONALE

Cancer treatment has improved considerably in recent years. One-year overall survival rates of breast and colon cancer patients are as high as 97% and 80% respectively (1). However, these advances have not yet been achieved for all malignancies. For hepatopancreatobiliary (HPB) cancers, surgical resection is often considered the only curative treatment which is only feasible in up to 25% of patients. The one-year overall survival rates of primary hepatic and pancreatic cancer patients in the Netherlands remain as low as 39% and 24% respectively (1). The dismal disease and treatment outcome is not solely affected by tumour characteristics. Additional factors, such as frailty, limit survival in cancer patients (2). Frailty is a state of increased vulnerability of an individual towards stressors, leading to an increased risk of developing adverse health outcomes (3). A hallmark sign of frailty is fatigue, which is the most frequently reported symptom in cancer patients, both during and after cancer treatment (4, 5). In gastrointestinal cancer patients, almost 30% of patients experience severe fatigue (6). Low physical activity is independently associated with severe fatigue before cancer treatment (6). During cancer treatment, rates of fatigue in various patient populations vary between 25 and 99% (7). After successful cancer treatment, 19 to 38% of disease-free cancer survivors remain fatigued, which underlines its persistent character (7, 8). In our own daily practice, we experience that fatigue in the first months is reported very frequently, particularly after major abdominal surgery for HPB cancer. Although the exact pathogenesis of fatigue remains to be revealed, disturbances in physiology, biochemistry and psychology are considered to contribute to this multifactorial symptom (9). Another key determinant of fatigue may be attributed to frailty, an age- and disease related skeletal muscle depletion (i.e. sarcopenia) (10). The prevalence of sarcopenia is common in HPB cancer patients, exceeding rates of 50% in our population (11). These patients experience muscle weakness that leads to physical impairment, increased fatigue and decreased quality of life (5). Furthermore, such sarcopenic and frail patients are more prone to a reduced therapy effect, complications of treatment and increased chemotherapy toxicity (12).

Although preoperative care (e.g. nutritional support and dietary consultation) and perioperative care (i.e. Enhanced Recovery After Surgery [ERAS]) have greatly improved short-term outcomes in surgical HPB cancer patients, the cancer itself, as well as the sequelae after surgical interventions or chemo(radiation)therapy may lead to physical and psychosocial impairment in cancer patients (13). As patients experience increased disease-related fatigue, fear or anxiety and depression, loss of muscle mass and strength, and subsequently a lower exercise tolerance, they are at great risk of spiralling down a vicious circle which progressively enhances these symptoms and further impairs their quality of life and self-management capacity (14, 15). These symptoms particularly occur in the early

postoperative phase. Although this series of events is well recognized as a potential course after major HPB surgery, monitoring of these patients' well-being after treatment frequently remains a neglected, unstandardized aspect of care. And if complaints of fatigue and weakness are recognized, it is still unknown to date how to offer these particular patients the best supportive care.

Since multiple dimensions (physical, emotional and cognitive) seem to be involved in fatigue, a multidimensional approach should be opted for (16). In patients who have been treated for cancer, psychotherapy was shown to significantly reduce fatigue (7). Particularly interventions with a more general approach, aiming at psychological distress, mood and physical symptoms, are effective in reducing fatigue (17) Furthermore, physical exercise has been demonstrated to reduce fatigue in cancer patients (18, 19) and cancer survivors (20, 21). The authors of a recent Cochrane review performed a meta-analysis comprising 56 studies (4068 participants with various cancers) that showed that physical exercise therapy can be regarded as beneficial for patients with cancer-related fatigue during the post-cancer therapy, particularly in patients with solid tumours (18).

A previous study of Van Weert et al. (22) compared the effect of combined physical training and cognitive-behavioural therapy with physical training only and no intervention on cancer-related fatigue in cancer survivors (63.2% breast cancer, 19.7% haematological cancer, 7.9% gynaecological cancer, and 9.2% other cancer). Physical training combined with cognitive-behavioural therapy and physical training alone had significant beneficial effects on fatigue compared with no intervention. Physical training was as effective as physical training with cognitive-behavioural therapy. The study population was not specified and likely included colorectal and breast cancer patients with relatively good prognosis. Furthermore, the physical exercise therapy program in this study included some elements of coping with fatigue, goal setting and exercise-relaxation balance activities, which may have reduced the effect of the cognitive-behavioural therapy. Solution focused therapy has also been proven effective in various patient populations. A great advantage of solution focused therapy is that a fewer number of sessions is needed to be effective compared with cognitive-behavioural therapy (23, 24). This translates in lower costs and could possibly lead to greater patient adherence.

Previous studies have been conducted in cancer patients with a relatively good prognosis, such as breast and colorectal cancer (20-22, 25-32). These populations generally reach a functional status after treatment that is comparable with pre-disease levels and patients may return to regular societal participation. Therefore, the results of these studies may not apply

to patients undergoing surgical resection of malignancies with a more dismal outcome and high morbidity even mortality in the first years after surgery, such as HPB cancer patients. In addition, HPB cancer patients experience a greatly impaired quality of life according to data from the European Organisation for Research and Treatment of Cancer (EORTC) (33). The mean global health status or quality of life in HPB cancer patients (all stages) on the EORTC Quality of Life Questionnaire-C30 is 56 points on a scale of 0-100, which is amongst the lowest scores for cancer patients. For example, breast cancer patients, colorectal cancer patients and the general population score 62, 61 and 71.2 respectively (33). Researchers in- (34) and outside (35-37) of our research group have demonstrated that quality of life is greatly impaired in HPB cancer patients, including candidates for surgery. In particular in patients with worsened survival the quality of life is lowest (35). Therefore, we aim to reduce fatigue complaints and increase quality of life in the early palliative phase of patients operated on for HPB malignancies.

1. OBJECTIVES

Primary objective

- To estimate the efficacy of cancer rehabilitation for patients with resectable hepatopancreatobiliary cancer to reduce general fatigue 12 months after discharge as measured by the MFI questionnaire.

Secondary objectives

- To assess the impact of rehabilitation on quality of life (EORTC-QOL C30), Frailty (GFI) and anxiety and depression (HADS).
- To describe the development of MFI-General Fatigue, MFI-Physical Fatigue, MFI-Mental Fatigue, MFI-Reduced Motivation and MFI-Reduced Activity measured preoperatively, at the start and end of the rehabilitation program and six and twelve months after surgery.
- To document the physical status of the patient by measuring the 6 minute walk test, grip and quadriceps strength, muscle mass (L3 muscle index), visceral adipose tissue and malnutrition risk (PG-SGA SF)..
- To describe the general performance of patients using the Karnofsky score, the sit-up and go test and accelerometer activity level measurements.
- To assess patients overall survival at 1, 3, and 5-years after surgery.
- To estimate the cost-utility of the rehabilitation program using QALYs (EQ-5D-5L, QLQ-C30), direct and indirect costs.

2. STUDY DESIGN

This study is a clinical, multi-centre randomized controlled trial.

2.1 Population (base)

All consecutive patients undergoing surgery for HPB malignancies (i.e. bile duct cancer, pancreatic cancer, hepatic cancer) in Erasmus MC (Rotterdam), AMC (Amsterdam), LUMC (Leiden), and UMCG (Groningen) will be considered for eligibility for study participation. Particularly these patients may benefit from the described intervention. After all, they have a dismal prognosis, but are considered fit enough to undergo surgery as this is the only hope for cure.

Approximately 120 HCC, 150 pancreatic cancer and 30 bile duct cancer patients undergo surgery in the four participating centres. Consequently, patient inclusion should be finished within something more than one year with an inclusion rate of 50%. Follow-up will be conducted for 5 years or until death to explore a possible association between the intervention and survival benefit.

2.2 Inclusion criteria

In order to be eligible to participate in this study, a subject must meet all of the following criteria:

- Undergoing curative intent surgery for HPB malignancies. Liver surgery will be defined as major if a left or right (extended) hemihepatectomy or if 3 or more segments are resected and minor if less than 3 segments are resected.
- Clinically suspect or histologically confirmed liver, bile duct or pancreatic carcinoma;
- Life expectancy of at least six (6) months;
- Resection performed
- Fatigue score ≥ 4 on a numeric rating scale (NRS) with scores of 0 to 10
- Able to read and understand the Dutch language;
- Written informed consent.

2.3 Exclusion criteria

A potential subject who meets any of the following criteria will be excluded from participation in this study:

- Bone metastases or other high risk of fractures;
- Not able to perform basic activities of daily living (ECOG ≥ 3);

- Decompensated heart disease, uncontrolled hypertension (systolic blood pressure > 200 mmHg or diastolic blood pressure > 110 mmHg), heart failure (NYHA Class II or greater) or chronic obstructive pulmonary disease causing fatigue;
- Living in nursing homes;
- Cognitive impairment;
- BMI <15 kg²/m², >5% weight loss per month or other health problems that would not allow physical exercise training;
- Anxiety or depression requiring psychiatric consultation;
- Cancer treatment in the previous 5 years (except basal skin cancer);
- Participation in other studies containing elements of physical exercise or psychological therapy.

2.4 Sample size calculation

MFI-General fatigue is the primary outcome of the study. To detect a medium difference in MFI-General fatigue (Cohen's $d = 0.50$) with a power of 0.80 and alpha of 0.05 (two sided), both groups should consist of 64 patients. With an expected 20% drop out rate (25), a total of 154 patients are needed.

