6.2 Randomisation, blinding and treatment allocation

Patients will be included on the preoperative surgical outpatient department. If at hospital discharge patients score ≥ 4 on the fatigue NRS , they will randomly be assigned to the treatment (rehabilitation program) or control (standard care) group in a 1:1 ratio.

Centralized stratified permuted block randomization will be performed by the Clinical Trial Center using the online ALEA software. The sample will be stratified based on organ (liver, pancreas, biliary tract) and organisation (EMC, LUMC, AMC, UMCG). Block randomisation within each stratum will be performed using variable block sizes ranging from 2 to 4. Neither patients nor therapists will be blinded for the treatment group. All therapists will be blinded for the NRS fatigue score that will be obtained before the start of the rehabilitation program.

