6.5 Replacement of individual subjects after withdrawal

Withdrawn subjects will not be replaced.

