8.1 Primary study parameter(s)

The primary end point is the MFI-General Fatigue score measured at 12 months after surgery as described earlier. Superiority of the intervention group versus the control group will be assessed using a Mann-Whitney U to test if the two independent samples come from the same distribution.

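### Section 2.4 inflates for 20% dropout by multiplying by 1.2 rather than dividing by 0.8, so 154 patients leave about 123 evaluable, not the 128 required

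*Protocol*

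**What the plan says.** Protocol section 2.4 sizes the trial for a standardised difference (Cohen's d) of 0.50 in MFI-General Fatigue, "with a power of 0.80 and alpha of 0.05 (two sided"). It concludes that "both groups should consist of 64 patients" and continues: "With an expected 20% drop out rate (25), a total of 154 patients are needed". It does not name the test behind the 64.

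Three other sections bear on this:
- Section 6.2 randomises to treatment or "control (standard care) group in a 1:1 ratio".
- Section 6.5 says: "Withdrawn subjects will not be replaced".
- Section 8.1 says: "Superiority of the intervention group versus the control group will be assessed using a Mann-Whitney U" test.

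Section 8 also plans an analysis adjusted for gender, age, education, marital status, disease stage and radicality of resection, and expects it to add power. Neither the calculation in 2.4 nor the test in 8.1 uses that adjustment.

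**The concern.** Section 2.4 treats 128 as the number of patients who must contribute a 12-month score. Dropout is a fraction of those randomised, so the total must be large enough that 80% of it is at least 128. Adding 20% of 128 instead gives a total that falls short of its own target once the planned loss occurs. Section 6.5 rules out making up the difference by replacement. The recruitment target and the stated power for the primary endpoint are therefore inconsistent with the inputs printed beside them.

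The choice of test raises a second question. If 64 is a t-test number and the primary comparison is a rank test, the sizing and the analysis do not correspond, and the rank test may need somewhat more patients.

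**Working it through.** **Inputs.** From section 2.4: d = 0.50, power 0.80, two-sided alpha 0.05, 64 per group, 20% dropout, total 154. From section 6.2: 1:1 allocation. From section 6.5: no replacement. From section 8.1: Mann-Whitney U.

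**1. Reproducing the 64.** A two-sample t-test (noncentral t) with these inputs needs n = 63.77 per group, rounded up to 64, with power 80.1% at 64. The normal approximation 2(1.96 + 0.84)²/0.50² gives 62.7, rounded up to 63. The match to 64 points to a t-test, but this is an inference.

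**2. Reproducing the 154.** 2 x 64 = 128, and 128 x (1 + 0.20) = 153.6, rounded up to 154. The correct inflation is 128/(1 − 0.20) = 160, or 80 per arm. The difference is 6 patients.

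**3. What 154 delivers at the stated dropout.** 154 x 0.80 = 123.2 evaluable, or 61.6 per arm, against 128 required.
- Normal approximation: Φ(0.50 x √(61.6/2) − 1.96) = Φ(0.815) = 79.2%.
- Noncentral t: 78.6%, which is about 1.4 points below the target.
- Effect detectable with 80% power: 0.50 x √(63.77/61.6) = 0.509, about 0.51.
- Dropout at which 154 still leaves 128: 1 − 128/154 = 16.9%.

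**4. The rank test, under an added assumption.** If scores are roughly normal and the groups differ by a location shift, the Mann-Whitney test has asymptotic relative efficiency 3/π = 0.955 against the t-test. Multiplying n per arm by 0.955 gives the equivalent t-test n:
- At 64 per arm, power is 78.3%.
- At 61.6 per arm, power is 76.7%.
- For 80% power, 63.77/0.955 = 66.8, so 67 per arm and 134 evaluable; 134/0.80 = 167.5, so 168 randomised.

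Simulation (20,000 runs per setting) agrees. With 61 against 62 patients, power is 77.4% for normal scores and about 76.3% for scores rounded and bounded to 4–20 (assumed means of 10 or 12, SDs of 4 or 4.5). At 64 per arm it is about 78% in all settings, and at 67 per arm about 80%.

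The protocol gives no distribution, so the range matters. At relative efficiency 1.0, nothing is lost beyond step 3: 78.6% with 154, and 160 needed. At a pessimistic 0.864, power with 154 is 72.4%, and 74 evaluable per arm are needed; 148/0.80 = 185, or 186 for equal arms. With heavier-tailed scores the rank test could gain power.

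**5. Covariate adjustment.** A linear model adjusted for a baseline score correlated r with the outcome acts roughly like a t-test with n/(1 − r²) per arm. At 61.6 per arm:

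| r (assumed) | equivalent n per arm | power |
|---|---|---|
| 0.2 | 61.6/0.96 = 64.2 | 80.2% |
| 0.3 | 61.6/0.91 = 67.7 | 82.3% |
| 0.5 | 61.6/0.75 = 82.1 | 88.9% |

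**The case against.** The strongest reply is that the loss is too small to matter. On the protocol's own figures, 6 patients and 1.4 points of power are at stake. The d of 0.50 is a conventional medium effect with no MFI standard deviation behind it, so a shift to 0.51 does not change what the trial can conclude. This stands as an argument about severity. It does not make 154 the right total for 20% dropout.

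Section 8 also plans covariate adjustment. Covariates explaining about 3.5% of outcome variance would restore 80% power at 123 evaluable in a linear model. That too bears on severity, but the superiority test in 8.1 is an unadjusted Mann-Whitney test, and 2.4 takes no credit for adjustment.

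A reader might go further and infer that, even with every planning assumption met, the type II error is about 23% and the trial is 14 patients short (168 against 154). The protocol does not support this as an unconditional statement. Section 2.4 names no test, and normality with a location shift is nowhere stated as a planning assumption. From the stated inputs and the inferred t-test alone, the type II error is about 21.4% (100% − 78.6%) and the shortfall is 6 patients.

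**Conclusion.** The dropout arithmetic in section 2.4 is wrong. The total should be 160, and 154 gives about 123 evaluable patients. That count rests only on the protocol's own 64 per group, 20% dropout and no replacement. The corresponding power of 78.6% additionally takes the t-test as the basis of the 64.

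The mismatch with the Mann-Whitney test is real but secondary. Its cost is about 2 points at 64 per arm and, combined with the dropout error, brings power to about 77%, provided that scores are roughly normal with a location shift.

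Severity is moderate. A stated number and its power need restating; the trial's ability to answer its question is not in serious doubt on this ground.

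**What to change.** Do one of the following in section 2.4:
- Correct the total to 160 (80 per arm).
- Keep 154 and state that, with 20% dropout, it gives about 123 evaluable patients and power of about 79% by t-test, or about 77% by Mann-Whitney under approximate normality.

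Either way, name the test on which the calculation rests. If 80% power is wanted for the Mann-Whitney test under approximate normality, the total is about 168.

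Restating costs one paragraph. The extra recruitment is small by section 2.1's own figures: about 300 operations, read here as annual, at 50% inclusion give 150 patients a year. Six more take about 6/150 x 52 = 2 weeks, and 14 more about 5 weeks.

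An option without extra patients is to make the primary analysis a linear model adjusted for the screening MFI-General Fatigue score, and to size on that model. The Appendix 2 schedule already collects this score before randomisation; the score two weeks after discharge comes after randomisation and should not be used as the baseline. This means amending both 2.4 and 8.1, because the Mann-Whitney test would be replaced. It reaches 80% at 123 evaluable if the correlation between screening and 12-month scores is about 0.2 or more. The protocol gives no such correlation, so it must be stated as an assumption.
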